### **Quality of Life**

Quality of life (QoL) will be measured in wart patients, using the Nepali version of the dermatology life quality index (DLQI) questionnaire before initiation of treatment and at the end of follow up. DLQI contains 10 questions that involves 6 sections: symptoms and feelings, daily activities, leisure, work and school, personal relationships and treatment. Questions 1 and 2 assess symptoms and feelings; 3 and 4, daily activities; 5 and 6, leisure; 7, work and school; 8 and 9, personal relationships and 10, treatment.

The DLQI consists of 10 questions. Each question is given 4 options from not at all effect (score 0) to very much effect (score 3). The minimum and maximum possible score, thus, is 0 and 30 respectively. The interpretation of the patients' score is done as follows:

#### Meaning of DLQI Scores

- 0-1 = no effect at all on patient's life
- 2-5 = small effect on patient's life
- 6-10 = moderate effect on patient's life
- 11-20 = very large effect on patient's life
- 21-30 = extremely large effect on patient's life

The clinically meaningful change or reduction in the DLQI score is measured as the change in score from one band to the other in the above-mentioned interpretation chart.

#### Statistical analysis

- Data handling: Data will be entered in Microsoft Excel 2010 (Microsoft Corporation, Redmond, Washington, USA) and statistical analysis will be done using Statistical Package for the Social Sciences 10.5 version (Chicago, Inc)
- 2. Coding: Alpha numerical code will be used
- Monitoring: Data will be entered after every day of work and supervised by guide.
- 4. Statistical analysis will be conducted as per both per-protocol and intention-to treat population (defined as all enrolled patients to whom study drug will be given; with the last observation carried forward) basis using two sided tests.

For *descriptive statistics*, percentage, mean, S.D., median, and minimum, maximum will be calculated along with graphical and tabular presentation.

For inferential statistics, statistical methods that will be used are as follow

- a. Chi square test and Fisher's exact test to compare the categorical data between the groups.
- b. Paired t test for comparing normally distributed continuous variables (pretreatment and post treatment DLQI) at different time point within the groups.
- c. Mann- Whitney U test to compare the not normally distributed variables (age, duration of illness, size, number)
- d. Kaplan–Meier curves to compare the response rate (complete, excellent, good or poor response) on each follow up visit (week 3, 6, 9, 12) between the groups.

Test of significance will be considered when value of  $p \le 0.05$ .

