# **Operational definition**

Wart - clinical diagnosis made by a dermatologist

Grades of clinical	Definition	VAS
improvement		score
Complete response	Complete disappearance of warts including	100%
	distant ones and skin texture at the site is	
	restored to normal	
Excellent response	Reduction in size and number including distant	75–99%
	ones and few residual warts still visible	
Good response	Some reduction in size only including that of	50-74%
	distant ones but no decrease in number of	
	warts	
Poor or no response	No significant change in size and number of	0–49%
	warts	
Recurrence	Recurrence during the study period	

Table no. 3 : Patient and physician global assessment using visual analog scale

score

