### Sample size

The study considers a 95% confidence interval, 80% power to estimate sample size. According to the literature review, it was found that 84.6% and 40% improvement were seen with IL MMR and IL Vitamin D respectively.

Now using the sample size estimation formula for 2 proportion

```
Now using the sample size estimation formula for 2 proportion

n = 2p(1-p) (Z\beta + Z\alpha/2)^2
```

n= sample size for each group

 $p_1 = 0.846$ 

 $p_{2} = 0.40$   $p = (p_{1} + p_{2})/2$   $Z_{\alpha/2} = 1.96 \text{ at } 95\% \text{ CI}$   $Z_{\beta} = 0.842 \text{ at } 80\% \text{ power}$ Using above formula, n= 18.54 Considering loss of follow up, sample size in each group= 30 Total sample size= **60** 

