#### **Group B**

All Group B patients will receive a maximum of 0.5 mL Inj. Vitamin D3 (600,000 IU; 15mg/ml) in each session after injection of IL lignocaine with 31 G insulin syringe. In cases of multiple warts, a maximum of 5 warts will be injected at a time. Amount of injection on each wart will depend on the size of each wart. The session will be done at 3 weekly intervals for a maximum of 5 sessions or until complete resolution of warts, whichever is earlier. 

Patient and physician global assessment using 'Visual Analog Scale score' and photographic comparison will be used to assess decrease in size and number of warts and thus the response to treatment. The clinical improvement will rated as complete response, excellent response, good response, poor or no response by the patient and physician global assessment using visual analog scale score at each visit taking baseline clinical photograph as controls. Immediate and late adverse effects of MMR vaccine and Vitamin D will be evaluated after each treatment session. Necessary investigations and intervention will be done if needed. Follow up will be made monthly for three months to detect any recurrence.

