# Follow Up

Number of visits	Date	Percentage decrease from	Recurrence (Yes/No)	Remarks
		baseline		
6 th				
7 th				
8 th				

	छाला रोग जीवनस्तर म	नूल्याङ्रन प्रश्नावली	
दर्ता नंः	मिति	डिएलक्यूआ इस्कोर	
नामः	रोग	ठेगाना.	

यो प्रश्नावली को उद्देश्य गत हप्तामा छालाको समस्या ले गर्दा तपाईको जीवनलाई के कतिको प्रभाव परेको छ भनि \_बुभ्চने हो । कृपया, प्रत्येक प्रश्नमा दिएका जवाफहरुमध्ये जुन उपयुक्त लाग्छ एउटा बॉक्समा \_\_\_]चेन्ह लगाउनुहोस् ।

۹.	गत हप्ता, तपाईको छाला कत्तिको चिलाउने, पोल्ने दुख्ने, वा विभर्ने गरेको थियो ?	धेरै थियो ।	Ť	C)	2
		ठिक्कै थियों।	20. 13		
		अनिकति थियो ।		8	
		पटक्कै थिएन ।		Ì	
ર.	गत हप्ता, तपाईको छालाको समस्याले गर्दा कत्तिको लज्जित वा आफैलाई अप्टेरो रो ने क्षिणो :	धेरै थियो ।			0
	પરવગો પંચા ?	ठिक्कै थियों।			
		अलिकति थियो ।		]	
		पटक्क थिएन ।			
₹.	गत हप्ता, तपाईको खालाले गर्दा किनमेलमा जोंदा, घरायसी काम गर्दा वा वगैचा	धेरै थियो ।	 	ek.	
	जादा कातका अण्ठयारी परका थिया ?	ठिक्कै थियो ।	15 17		
		अलिक ति थियो ।			% 
		पटक्क थिएन ।	1	महत्व थिएन	
8.	गत हप्ता, तपाईको छालाले गर्दा आफनो पहिरनमा कत्तिको प्रभाव परेको थियो ?	धेरै थियो ।	2		3
		ठिक्कै थियो ।			
		अलिकति थियो ।			
		पटक्क ° थिएन ।		महत्व थिएन	
X.	गत इप्ता, तपाईको छालाले गर्दा सामाजिक वा अतिरिक्त कियाकलापमा कत्तिको	धेरै थियो ।	8		2
	असर परेको थियो ?	ठिक्कै थियों।			
		अनिकति थियो ।	30 (		
				महत्व थिएन	
8		पटक्क थिएन ।			
Ę .	गत हप्ता, तपाइंको छालाले गर्दा तपाइंलाई खेलकुद गर्न कत्तिको कठिनाई परेको किन्ने 2	धेरे थियों ।			
	1991.2	ठिक्कै थियो ।	8		
		अनिकति थियो ।		AND	36
		पटक्क थिएन ।		महत्व थिएन	·2
6	गत हप्ता, तपाईको खालाको समस्याले गर्दा आफनो काम वा पढाईमा रोक लागेको	थियो ।			2
	थियो ?	थिएन ।		महत्व थिएन	
20°	यदि "थिएन" भने गत हप्ता तपाईको काम अथवा पढाईमा कत्तिको समस्या आएको	ठिक्कै थियो ।			
	थियो ?	अनिकति थियो ।			
		प्रबद्ध शिएन ।			
80  		and former a			
б.	गत हप्ता, तपाइका छालाका समस्याल गदा तपाइका जामान/जामता, कुनपान नजिकको साथी, अथवा नातेदारसंग कतिको समस्या भएको थियो ?	धरायया ।			
		ठिक्के थियों ।			
		अनिकति थियो ।		गरहर विवास	
		पटक्क थिएन ।		महत्व । थएन	
٩.	गत हप्ता, तपाईको छालाको कारण यौनजन्य समस्या कतिको परेको थियो?	धेरै थियो ।			
		ठिक्कै थियो ।			
		अनिकति थियो ।			
		पटक्क' थिएन ।		महत्व थिएन	
90.	गत हप्ता, तपाईको छालाको उपचारमा कतिको समस्या भोग्नु परेको थियो जस्तै :	धेरै थियो ।	1		
	घर फाहार हुनु अथवा समय वडी लागेको थियों ?	ठिक्कै थियों।			
		अलिकति थियो ।			
		गतका विगाल ।		महत्व थिएन ।	
		नदनक विष्य ।			

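### Carrying the last observation forward enters a DLQI change of exactly zero for every treated patient without the final DLQI, so DLQI needs its own missing-data rule

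*Combined protocol and SAP*

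**What the plan says.** Item 4 of Statistical analysis (repeated in the protocol summary, item 10(k)) plans a per-protocol and an intention-to-treat analysis. The latter covers every enrolled patient who receives study drug, "with the last observation carried forward". No outcome is excepted. No other missing-data method and no sensitivity analysis is given, and the per-protocol set is not defined.

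For quality of life, the Nepali DLQI is completed "before initiation of treatment and at the end of follow up" (Quality of Life). Its only named test is in item b: "Paired t test for comparing normally distributed continuous variables (pretreatment and post treatment DLQI) at different time point within the groups". Under Meaning of DLQI Scores, a clinically meaningful change is a move from one score band to another.

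For recurrence, the text under Group B says: "Follow up will be made monthly for three months to detect any recurrence". Table 3 (Operational definition) lists recurrence beside the response grades and defines it only as "Recurrence during the study period". The annexed proforma has a yes/no field for it on the Follow Up form, which covers visits 6 to 8, and nowhere else.

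On expected loss, the Sample size section says only: "Considering loss of follow up, sample size in each group= 30".

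**The concern.** Carrying the last value forward presupposes that some value was taken after baseline. For the response grades there is one at each session. For DLQI there is none between baseline and the end of follow-up. For this outcome the rule is therefore baseline carried forward: the patient is recorded as unchanged whatever happened. The paired t test would run on a mixture of real changes and manufactured zeros. By the band rule, each such patient would also be counted as not improved.

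This matters because absence need not mean failure. Injections stop at complete resolution, and the summary (item 17) says that patients bear the cost. Someone who clears and does not come back would be recorded as a complete responder and, in the same dataset, as having had no change in quality of life.

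Recurrence raises a related but smaller question. If complete response is carried forward for a cleared patient who misses visits 6 to 8, not having looked is treated as not having recurred.

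**Working it through.** **1. The plan's own figure.** Inputs from Sample size: p1 = 0.846, p2 = 0.40, Z = 1.96 and 0.842.

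- p = (0.846 + 0.40)/2 = 0.623
- n = 2 × 0.623 × 0.377 × (0.842 + 1.96)² / (0.846 − 0.40)² = 0.4697 × 7.8512 / 0.1989 = 18.54

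This reproduces the stated 18.54, or 19 per group. Raising 19 to 30 leaves room for a loss of 1 − 19/30 = 11/30 = 36.7%. The plan does not state this rate. It is used below only as the top of a range, with 10% and 20% as further assumed values.

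**2. Effect on the mean DLQI change.** Let d be the share of treated patients without the final DLQI, C the mean fall in DLQI among those with both forms, and D the true mean fall among those without the final form.

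- True mean = (1 − d)C + dD
- Mean with the baseline carried forward = (1 − d)C + d × 0 = (1 − d)C
- Error (reported minus true) = −dD

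So the direction depends on D:

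- D = C (would have improved like completers): reported/true = 1 − d.
- D = 0 (no change): no error.
- D < 0 (worsened): the report is too favourable. For example, with C = 5, D = −2 and d = 0.20 (all assumed), the true mean is 0.8 × 5 − 0.2 × 2 = 3.6, but 0.8 × 5 = 4.0 is reported.

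**3. Illustration for D = C.** The documents give no expected DLQI change or SD. Assumed here: mean fall 5 points, SD of change s = 5, 30 treated patients per group. With the zeros included, the SD is √[(1 − d)s² + d(1 − d)C²].

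| Assumed loss d | Reported/true | Reported mean (true 5) | t with zeros, n = 30 | Observed pairs | t, observed pairs |
|---|---|---|---|---|---|
| 10% | 90% | 4.5 | 4.95 | 27 | 5.20 |
| 20% | 80% | 4.0 | 4.47 | 24 | 4.90 |
| 36.7% | 63% | 3.2 | 3.73 | 19 | 4.36 |

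With an assumed mean fall of 3 points and 36.7% loss, the reported mean is 1.9 and t is 2.46, against 2.62 in the observed pairs. With 8 points, the mean is 5.1 and t is 5.01, against 6.97.

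The test remains significant in all these cases, so the damage is to the estimate rather than to the yes/no result. Keeping all 30 patients also brings no gain in power. With zeros, t = √[n(1 − d)] × C/√(s² + dC²), which is always below the observed-pairs value √[n(1 − d)] × C/s.

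**4. Recurrence.** If unseen cleared patients are kept as cleared, the reported proportion is r(1 − u), where r is the true proportion and u is the share of would-be recurrences that fall in patients not seen again. This can only be at or below r. The documents give neither a three-month r nor any u, so no figure is put on it.

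**The case against.** The strongest reply is about scope. DLQI is a secondary objective, recurrence is not a listed objective at all, and the comparison of response between arms is not what this point concerns. A per-protocol analysis is also planned, and for DLQI it would in effect use observed pairs. All of this is fair. It limits the importance of the point, but the per-protocol set is undefined, and the intention-to-treat DLQI result would still contain the zeros.

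Several stronger readings are tempting, and the documents do not support them:

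- **That DLQI benefit is always understated.** This holds only if patients without the final form had improved. Section 2 of the working shows no error, or a flattering one, otherwise.
- **That unequal loss would create a false treatment difference in DLQI.** The only planned DLQI test is within groups, and the objective is to determine DLQI in wart patients. There is no planned between-arm DLQI comparison to distort.
- **That the plan counts unseen cleared patients as free of recurrence.** The yes/no field exists only on the visit 6 to 8 form, so a patient who misses all three visits has no recurrence value to carry. The plan implies that complete response would be carried instead, but does not say so.
- **That the recurrence undercount can be sized by joining the 12% rate in the literature review to a 37% loss.** That rate covers six months, while this trial follows patients for three. It is also the highest in the review, where other studies report none, 3.7% or 5.26%. The 37% is a whole-trial allowance, not the share of cleared patients who skip later visits.
- **That the rule contradicts the planned Kaplan–Meier curves.** Item d does not say that carried-forward values feed the curves. This is unspecified, not contradictory.

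**Conclusion.** The point holds for DLQI. As written, the rule gives a change of exactly zero to every treated patient without the final DLQI; patients never given study drug are outside the population and are not affected. If those patients would have improved like completers, the reported mean change is 90%, 80% or about 63% of the true one at losses of 10%, 20% or 37%. The loss rates, the DLQI changes and the SD are assumptions. The zero itself follows directly from the two-point DLQI schedule.

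The recurrence point is secondary. The plan does not say how cleared patients who are not seen are handled, and the natural reading of its rule can only undercount.

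Both should be settled before the data are analysed. Neither affects the sample size.

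**What to change.** Amend item 4 of Statistical analysis, and its copy in summary item 10(k), so that each outcome has its own rule:

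1. **DLQI.** Exempt it from carrying forward. The main analysis uses patients with both the baseline and the end-of-follow-up score. Add, as a sensitivity analysis, multiple imputation using baseline DLQI, arm and last response grade. Report the number without a final DLQI in each arm, and apply the band-change summary to observed pairs only.
2. **Recurrence.** Report it only among patients who cleared, as time to recurrence censored at the last attended visit. Show how many cleared patients were not seen at visits 6 to 8.
3. **Complete response.** Fix the time point as the end of treatment. A patient documented as cleared by then stays a responder, even if later visits are missed. A patient who leaves before documented clearance counts as a non-responder. Without the time point, a missing-equals-failure rule could turn a documented clearance into a failure.

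The cost is analysis-plan wording, a little more analysis work, and fewer patients in the main DLQI analysis. The number of patients, the visits and the treatment do not change.

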## INTRODUCTION

Warts are papulonodular epidermal lesions with a horny or papillomatous surface caused due to infection by human papillomavirus (HPV).

Cutaneous warts occur in 7% to 10% of the general population, with a maximum incidence between the ages of 12 and 16 years. Warts can persist as it is for years and then spontaneously clear at any time from a few months to a few years. In children, clearance can occur even after only a few months, with 50% at 1 year and about 65%–78% by 2 years.  The rate of clearance is influenced by factors like virus strain, host immune status, extent, and duration of warts 

HPVs are ubiquitous, epitheliotropic non-enveloped small double-stranded DNA viruses. Over 150 types of papillomavirus have been identified based on DNA studies and serological detection of type-specific antibodies against HPV capsid antigens. Among them verruca vulgaris or common warts are usually caused by Human Papilloma Virus (HPV) types 1, 2, 4, 27 or 57, and plane warts by HPV types 3 or 10.

The transmission of warts occurs from direct contact or indirectly via fomites. Usually, warts spread in swimming pools and bathrooms as the skin is macerated and is more prone to minor abrasions and infections thus serving as conduits for HPV to the basal keratinocytes, the primary targets for HPV infection.  There they undergo a latent phase of slow replication and then induce epidermal hyperplasia and hyperkeratosis as the epidermis grows superficially. 

The destructive therapies in treatment of wart include salicylic acid, trichloroacetic acid, cryotherapy, silver nitrate, phenol, cantharidin, surgical interventions and lasers; antiproliferative agents include bleomycin, vitamin D analogs, podophyllin, podophyllotoxin, and 5-fluorouracil; antiviral agents include cidofovir and retinoids. Other modalities include hypnotherapy, acupuncture, local hyperthermia, therapeutic vaccination, and combinations of the previous agents.

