### **Inclusion criteria**

- 1. Clinically diagnosed patients who have more than three warts or single wart in difficult to treat sites (periungual, palms and soles)
- 2. Age >/= 12 years

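### Response is compared between arms with no adjustment for wart extent or duration, so a chance imbalance between two groups of 30 would go uncorrected

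*Combined protocol and SAP*

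**What the plan says.** All references are to the combined protocol and SAP.

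- **Statistical analysis, item 4a:** chi-square and Fisher's exact tests are used "to compare the categorical data between the groups". Item 4d adds Kaplan–Meier curves for response. No regression model or stratified test is named.
- **Statistical analysis, item 4c:** the Mann–Whitney test is used "to compare the not normally distributed variables (age, duration of illness, size, number". This is the only use the analysis section makes of duration and number.
- **Introduction:** "The rate of clearance is influenced by factors like virus strain, host immune status, extent, and duration of warts".
- **Inclusion criteria:** patients enter with "more than three warts or single wart in difficult to treat sites (periungual, palms and soles".
- **Operational definition:** a complete response needs every wart gone, distant ones included, with normal skin texture.
- **Methodology:** allocation is by computer-generated random numbers. Neither stratification nor blocking is mentioned.
- **Methodology and Proforma:** site, size and number of lesions are recorded at baseline, and the proforma also has duration.

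**The concern.** The two entry routes put different demands on the endpoint. A patient with one wart must clear one lesion; a patient with more than three must clear all of them. Against that, the single wart is at a site the protocol itself regards as hard to treat. Either way, patients differ at baseline in extent, which the protocol names as relevant to clearance, and they also differ in duration.

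Neither the allocation nor the analysis protects the comparison of arms against imbalance in these factors. Comparing duration or number between arms by Mann–Whitney may reveal an imbalance, but it does not correct the response comparison for it. If the one trial actually run turns out visibly unbalanced, the result is open to challenge and the plan has no pre-specified answer. An adjustment chosen after the imbalance has been seen would be data-driven.

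**Working it through.** **Inputs from the documents.** Response 84.6% (MMR) and 40% (vitamin D), Sample size section: "84.6% and 40% improvement were seen with IL MMR and IL Vitamin D respectively". Two-sided 5% level and 80% power: "basis using two sided tests", "The study considers a 95% confidence interval, 80% power to estimate sample size". Enrolment of 30 per arm.

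**Assumed inputs.** Prevalence of the prognostic factor (50% unless stated) and the points by which it shifts clearance. The documents give neither.

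**1. The plan's own figure.** With p = (0.846 + 0.40)/2 = 0.623 and the usual denominator:

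n = 2p(1−p)(Zβ + Zα/2)²/(p1−p2)² = 2 × 0.623 × 0.377 × (0.842 + 1.96)²/0.446² = 18.54 per group.

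This reproduces the stated value. At 30 per arm, power for these rates is 96.5% (normal approximation).

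**2. Chance of imbalance.** Let XA and XB be independent Binomial(30, 0.5) counts of patients with the factor. A 20-point gap is 6 patients, and P(|XA − XB| ≥ 6) = 15.5%. At 30% prevalence it is 12.0%, and at 20% prevalence 7.5%. For at least one of two independent factors at 50% prevalence it is 1 − (1 − 0.155)² = 28.6%.

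**3. Displacement of the observed difference.** Imbalance × shift: 0.20 × 20 = 4 points, 0.20 × 30 = 6, 0.20 × 40 = 8. The standard error at the design rates is √(0.846 × 0.154/30 + 0.40 × 0.60/30) = 11.1 points. At 72% versus 40% it is 12.1 points.

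**4. False positives under no treatment difference.** Simulation with 30 per arm, one factor at 50% prevalence and a common true response rate of 50% (assumed), 200,000 trials per scenario. The tests are the unadjusted chi-square and the Cochran–Mantel–Haenszel (CMH) test without continuity correction, stratified on the factor.

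| Assumed shift | Unadjusted, all trials | Unadjusted, trials with ≥20-point imbalance | CMH, same trials |
|---|---|---|---|
| 20 points | about 5% | about 6.5% | about 5% |
| 30 points | about 5% | about 8% | about 5% |
| 40 points | about 5% | about 10% | about 5% |

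**5. Power, unadjusted versus uncorrected CMH, one factor.** The 72% is an MMR rate from the protocol's Table 1; 40% is its planning rate for vitamin D.

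| Assumed shift | 84.6% vs 40% | 72% vs 40% |
|---|---|---|
| 0 | 96.1% → 96.0% | 72% → 71% |
| 20 points | 96.3% → 97.2% | 72% → 73% |
| 30 points | 96.3% → 98.2% | 72% → 76% |
| 40 points | not possible (84.6 + 20 exceeds 100) | 72% → 80% |

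Stratifying on two factors at once (four strata) costs slightly more when neither matters: 96.3% → 95.5% at the design rates and 71% → 69% at 72% versus 40%. If both have an assumed odds ratio of 5, the figures are 96.3% → 98.0% and 72% → 79%.

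**6. Effect of a continuity correction.** With a non-prognostic factor, a continuity-corrected CMH lowers power from 96% to about 93% at the design rates, and from 72% to between 61% and 62% at 72% versus 40%: a loss of 3 to 11 points.

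**The case against.** The strongest reply is that the unadjusted comparison is valid under randomisation and well powered as planned. Both statements stand. Overall type I error is about 5%, and power is about 96% at the design rates. A reader might infer that the plan loses power by not adjusting; at its own rates it loses at most about 2 points for shifts up to 30 points. A gain of several points needs both a smaller true difference and a strong factor. A smaller difference is not remote: the Rationale cites MMR clearance from 70.4% to 82.4% and vitamin D clearance from 40% to 90%, so 84.6% versus 40% pairs a rate above the first range with the bottom of the second. At 70.4% versus 40%, power is about 67% unadjusted, and 68%, 71% or 75% stratified for 20-, 30- or 40-point factors.

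The second reply is that large shifts lack support in the documents. This also stands. The one within-trial contrast by wart type, in the cited randomised MMR trial, is 80% (recalcitrant) versus 84.6% (multiple). That is 4.6 points, although it is not the contrast between the two entry routes. At 4.6 points a 20-point imbalance displaces the result by only 0.20 × 4.6 = 0.9 points.

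Third, a reader might take the Introduction to say that entry route drives clearance. It says that extent and duration are among the influences, and it says so next to remarks on spontaneous clearance. Entry route is an inference from extent, site and the endpoint definition, and the direction of its effect is unclear.

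Fourth, a reader might infer that the Mann–Whitney tests are meant to decide whether to adjust. The plan contains no such rule, and item 4c does not even say that the comparison is at baseline.

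None of this supplies an answer if the arms turn out unbalanced.

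**Conclusion.** The concern holds as a gap in pre-specification. Response is compared without adjustment, the protocol itself names extent and duration as influences on clearance, the data are already collected, and no stratified randomisation is stated.

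What is at stake is the credibility of the result in the roughly one trial in six or seven (15.5%) where a factor with 50% prevalence is unbalanced by 20 points or more. There the false-positive rate would be about 6.5% to 10% instead of 5%, for assumed shifts of 20 to 40 points. With a weaker or rarer factor the problem is smaller.

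The documents do not support a reading that the planned test is invalid, that its overall error rate is inflated, or that material power is lost at the planned effect. At 72% versus 40%, adjustment changes power by about −1 to +4 points for shifts of 0 to 30 points, and by +8 points for a 40-point shift. All these figures rest on assumed prevalence and prognostic strength.

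**What to change.** Before data are seen, pre-specify one adjusted analysis of complete response:

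- A CMH test, stated to be without continuity correction, stratified by entry presentation (single difficult-site wart versus more than three warts). The recorded number and site of lesions define the strata.
- The stratified risk difference with its 95% CI.
- As sensitivity, a logistic model with treatment, presentation and wart duration. Sixty patients do not support a longer list of covariates.

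Making this the main comparison is preferable. Naming it as a supportive analysis beside the chi-square/Fisher test is the minimum. State also that the covariates are fixed in advance and do not depend on any test comparing the arms at baseline.

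The cost is one extra test and one model on data already collected. If presentation turns out not to be prognostic, the uncorrected CMH test loses under 1 point of power. A continuity-corrected version would lose 3 to 11 points, so the plan must name the version.

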# Secondary Objective:

- To determine the clinical and demographic profile of patients with different types of warts visiting Dermatology outpatient department of BPKIHS
- 2. To determine the side effects of IL MMR vaccine and IL Vitamin D in treatment of wart
- 3. To determine Dermatology life quality index (DLQI) in wart patients.

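### DLQI is tested only by paired t tests within each arm; no between-arm DLQI comparison is specified, although the arms are randomised and DLQI is collected twice

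*Combined protocol and SAP*

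**What the plan says.** - **Objective.** The third secondary objective is "To determine Dermatology life quality index (DLQI) in wart patients". It names no arm and no comparison.
- **Collection.** The Quality of Life section has DLQI measured "before initiation of treatment and at the end of follow up", with no restriction to one group. The Methodology section assigns patients to Group A or B from a computer-generated random number table.
- **Test for DLQI.** Statistical analysis, item 4b (repeated in item 10(k) of the protocol summary): "Paired t test for comparing normally distributed continuous variables (pretreatment and post treatment DLQI"), "at different time point within the groups".
- **Other tests.** Item 4a is general: "Chi square test and Fisher's exact test to compare the categorical data between the groups". Item 4c is "Mann- Whitney U test to compare the not normally distributed variables (age, duration of illness, size, number"). Item 4d uses Kaplan–Meier "curves to compare the response rate (complete, excellent, good or poor response) on each follow up visit". None of the three names DLQI.
- **Meaningful change.** The section on the meaning of DLQI scores defines a meaningful change as a move from one score band to another. No analysis is attached to that definition.

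**The concern.** The trial randomises, and it collects what a randomised comparison of quality of life needs: a baseline and a final score in both arms. The one test given to DLQI then sets the randomisation aside and compares each arm with its own past.

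A before-after change in one arm is not a treatment effect. The Introduction says that warts can clear spontaneously at any time, and that in children about half clear by one year. In the Review of Literature, control patients also improve: 5% complete clearance under saline in the vitamin D3 RCT, and 30% partial response among controls in the plantar wart trial. Patients are eligible from about age 12, and a full course of five sessions three weeks apart (12 weeks from first to last) plus three months of follow-up puts the final DLQI about six months after baseline. Some improvement could therefore occur without either drug. The protocol summary lists control groups as not applicable, so there is no untreated arm to show how much. The contrast between the two randomised arms is the only protected treatment comparison available.

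At stake is what the thesis can say about quality of life by treatment. With only the planned test it would have two within-arm p-values and no estimate of the difference between arms.

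**Working it through.** **1. Which analyses could reach DLQI between arms?**

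| Item | Comparison | Variables named | DLQI named? |
|---|---|---|---|
| 4a chi-square / Fisher | between groups | categorical data, unspecified | no |
| 4b paired t | within groups | DLQI before and after | yes |
| 4c Mann-Whitney | not stated | age, duration, size, number | no |
| 4d Kaplan–Meier | between groups | response grades | no |

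No independent-samples test, ANCOVA or comparison of DLQI change between arms is named.

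**2. What do two within-arm tests say about a treatment difference?** Suppose both arms have the same true improvement and each paired test has power p. The arms are independent, so

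P(exactly one arm significant) = 2p(1-p)

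- p = 0.50: 2 × 0.50 × 0.50 = 0.50
- p = 0.80: 2 × 0.80 × 0.20 = 0.32
- p = 0.95: 2 × 0.95 × 0.05 = 0.095

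The maximum is 50%, and the figure falls as power rises. The documents give no DLQI standard deviation or expected change, so these powers are assumptions.

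**3. Check by simulation.** Settings: 30 per arm, normal change scores, the same true change in both arms, 5% two-sided tests, 20,000 runs. True changes are in SDs of change and are assumed.

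| True change | Power of each paired test | Exactly one arm significant | Direct between-arm t test rejects |
|---|---|---|---|
| 0.20 | 19% | 31% | 4.8% |
| 0.36 | 48% | 50% | 5.2% |
| 0.50 | 75% | 37% | 4.9% |
| 0.70 | 96% | 8% | 5.0% |

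The discordance follows the formula. The direct comparison keeps its 5% error rate throughout.

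**4. Was the trial sized for DLQI?** No. The plan's sample size uses response rates of 0.846 and 0.40, so p = 0.623. With the squared difference as denominator (not visible in the extracted formula):

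n = 2 × 0.623 × 0.377 × (0.842 + 1.96)² / (0.446)² = 3.688 / 0.1989 = 18.54

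This reproduces the stated figure, which was then raised to 30 per group. It concerns response only.

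**5. What precision would a between-arm DLQI comparison have?** The difference detectable with 80% power at two-sided 5%, in SDs of the final score (normal approximation):

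- 30 per arm, unadjusted: 2.802 × √(2/30) = 0.72 SD
- 25 per arm: 2.802 × √(2/25) = 0.79 SD
- 20 per arm: 2.802 × √(2/20) = 0.89 SD
- 30 per arm, ANCOVA: 0.72 × √(1 − ρ²) = 0.69, 0.63 and 0.52 SD for an assumed baseline-final correlation ρ of 0.3, 0.5 and 0.7

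Only fairly large differences would be detected reliably.

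**The case against.** The strongest reply is that the plan leaves no stated objective unanswered. The DLQI objective is only to determine DLQI in wart patients, whereas the primary objectives say plainly when a comparison is meant. The hypotheses concern treatment of warts, and the listed outcome measure is response rate. A before-after test is a reasonable companion to a descriptive aim. This stands: the gap contradicts no objective and does not touch the primary comparison.

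Four stronger readings are tempting, and the documents do not support them.

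- *A reader might infer that quality of life can never be compared between arms under this plan.* Moving between DLQI bands is a categorical outcome, and the general wording of item 4a could cover it. The accurate statement is that no such comparison is specified. Relying on item 4a would also leave the choice of outcome open until analysis, lose information through banding and make no adjustment for baseline.
- *A reader might infer that the authors will contrast the two within-arm p-values.* Nothing in the plan says so. The risk is that those p-values would be the only arm-specific DLQI results to hand.
- *A reader might blame regression to the mean.* Entry depends on wart number, site and age, with no DLQI threshold, so support for this is weak. Natural clearance is the documented reason.
- *A reader might take 50% as the typical size of the problem.* It is the maximum. If improvement is large, as the response rates assumed for the sample size make plausible, paired power may be high and discordance below 10%.

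Nor would the efficiency of ANCOVA over change scores measure this defect, since the plan contains neither method.

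**Conclusion.** The point holds as an omission in a secondary analysis. The only inference specified for DLQI is within arm and does not use the randomised contrast. Read alone, it cannot separate a drug effect from natural clearance, and two such tests cannot support a treatment difference. If both arms improve equally, exactly one would be significant in 9.5% to 50% of trials for paired power between 95% and 50%. Those powers are assumed, because the documents give no DLQI variance or expected change. That range only matters if the two p-values are contrasted; the absence of a between-arm estimate does not depend on it. The primary response comparison is unaffected, and the amendment is worth making before analysis because the data are already planned.

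**What to change.** Add to item 4b, and to its copy in item 10(k) of the protocol summary:

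- Compare end-of-follow-up DLQI between groups by ANCOVA with baseline DLQI as covariate, and report the adjusted mean difference with its 95% CI.
- If the scores are clearly non-normal, compare change in DLQI between groups by Mann-Whitney. Item 4b depends on normality and currently has no fallback for DLQI.
- Keep the paired tests as description of each arm, and state that no treatment difference will be inferred from separate within-arm p-values.
- Note that the trial was not sized for DLQI, so the confidence interval carries the interpretation and a non-significant result does not show equivalence.

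One detail to settle at the same time: DLQI is taken only twice, so the plan's last-observation-carried-forward rule would replace a missing final score with the baseline score, and the new analysis would inherit this.

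Cost: one extra secondary analysis on data already to be collected, with no new visits or patients. The downside is limited precision, with about 0.5 to 0.7 SD detectable at 80% power with 30 per arm, and less precision after dropout.
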